1. TITLE

Identifying and examining the effects of source and presentation on responses to electronic cigarette public education messages in young adult vapers and non-vapers - Part 1

2. EXTERNAL IRB REVIEW HISTORY*

NA

3. PRIOR APPROVALS:

NA

Conflict of Interest (COI):

NA

Clinical Engineering Department:

N/A

Biohazardous Agents:

NA

Radiation:

NA

Students as Subjects:

NA

Data Science Core & Recruitment Core:

NA

UMCCTS Protocol Review Committee (PRC)

NA

4. OBJECTIVES*

The goal of the study is to conduct a crowdsourced testing to examine the effects of source and presentation of e-cigarette educational messages among young adults who currently vape and do not vape but are susceptible. The objectives are to examine young adults' self-reported responses toward message source (expert vs. peer), message sidedness (one-sided vs. two-sided), and messages combining both (source x message sidedness) about anti-e-cigarette messages.

Aim 1: To determine the optimal message source and presentation type for young adult vapers and susceptible non-vapers to increase acceptance of e-cigarette education messages and e-cigarette harm perceptions.

H1. Vapers will report greater message acceptance and harm perceptions than peer and two-sided messages.

Aim 1: Which message source and sidedness strategy is effective for susceptible non-vapers?

INVESTIGATOR STUDY PLAN - REQUIRED

H1. Susceptible non-vapers will report greater message acceptance and harm perceptions to expert and one-sided messages.

Please note that all procedures will be conducted online and there will be no direct in-person interaction between researchers and participants.

5. BACKGROUND*

Young adults (18-24-year-olds) in the U.S. have the highest rates of e-cigarette use (vaping),¹ with 16-19% of this population identifying as current users, 44-48% ever users, and 11-16% susceptible never users.² Vaping can lead to nicotine addiction and initiation of cigarette smoking³⁻⁷ and is associated with cognitive and affective disorders among young adults.⁸ The U.S. Food and Drug Administration (FDA) has prioritized educating about the health harm of vaping among young adults. However, young adults may avoid^{9,10} or reject¹¹ the current education messages, especially if they currently vape¹²⁻¹⁴ or perceive the messages as “controlling.”¹⁵ It is urgently needed to increase acceptance of e-cigarette education messages¹⁶ to influence their e-cigarette harm perceptions and vaping behaviors.¹⁷⁻²⁰

Using a trusted source²¹⁻²⁴ and presenting messages appropriately^{25,26} can increase message acceptance. According to persuasion theories, one’s tobacco use status may influence individuals’ response to a source and presentation of messages because vapers and susceptible non-vapers differ in their attitudes and personal relevance regarding tobacco use.^{25,27-29} Unfortunately, no research has yet examined the impact of a message source^{22,30} and presentation^{25,31,32} on young adults’ responses to e-cigarette education messages based on their vaping status. Evidence from research with cigarette smokers suggests that vapers will respond defensively to e-cigarette education messages, but susceptible non-vapers will not.^{12,33} Vapers may trust a tobacco health information source with similar attributes (e.g., peer young adults)^{29,34} and accept messages with balanced perspectives that both present negative health effects of vaping and acknowledge their potential reasons for vaping (two-sided; e.g., “vaping can be appealing if others are using it, but it can harm your health”).^{25,31,35} On the other hand, susceptible non-vapers may trust a source with credentials (e.g., scientists)³⁶⁻³⁸ and accept information-only messages (one-sided; e.g., “vaping can harm your health”).^{13,35} Thus, it is critical to understand and use a trusted source and present messages that are appropriate for vapers and susceptible non-vapers to optimize vaping cessation and prevention efforts, making it an important area of study to improve current messaging.

The proposed research is guided by biobehavioral theories of tobacco regulatory science,^{39,40} psychology,^{15,41} and communication.^{42,43} By using previously tested education messages,⁴⁴ we will determine an optimal combination of message source and presentation type to increase message acceptance and e-cigarette harm perceptions. We will compare the effects of two sources (expert and peer) and two message presentation types (one-sided and two-sided) for young adult vapers and susceptible non-vapers. We will use crowdsourcing (N=800) for post-test self-report measures (message acceptance, harm perceptions) to determine optimal messaging. The goal of this study is to determine optimal message source and presentation for young adult vapers and susceptible non-vapers to increase message acceptance and harm perceptions using crowdsourcing.

6. INCLUSION AND EXCLUSION CRITERIA*

We will recruit 800 young adults between the ages of 18 and 24 years old (50% current vapers and 50% susceptible non-vapers) via Prolific crowdsourcing platform. Prolific is an on-demand,

INVESTIGATOR STUDY PLAN - REQUIRED

self-service data collection. Prolific helps you recruit high quality research participants to take part in your study, survey or experiment (<https://www.prolific.com/>). Participants will be 18 and older and based in the United States. We will not include participants who are not fluent in English. Prisoners or adults who are unable to consent will not be included in the study. Pregnant women may be in the study if they choose, but we will not seek pregnant people to be in the study.

We will screen for e-cigarette use susceptibility of non-vaper participants. Potential participants will be recruited from Prolific and directed to a screener survey. Participants are susceptible to e-cigarette use if they respond to the tobacco use susceptibility question items (Have you ever been curious about using an e-cigarette? (1=Not at all curious, 5=Very curious); How likely is that you will try an e-cigarette, even one or two puffs, any time soon? (1=Very unlikely, 5=Very likely); How likely is that you will try an e-cigarette, even one or two puffs, any time during the next year? (1=Very unlikely, 5=Very likely); If one of your best friends were to offer you an e-cigarette, would you use it? (1=Very unlikely, 5=Very likely) in anything other than 1=not at all/very unlikely. We will collect participants' Prolific ID, a unique anonymous identifier, to create the list of eligible participants to participate in the 20-minute study. We expect that we will need 640 number of people identified as non-vapers to complete the screener and to have a complete sample for the 20 minute study, which will consist of susceptible non-vapers and vapers.

Prolific.com provides individuals who are eligible for each of the categories we are recruiting. We do not need to screen the participants for this. We can just click our preferences for those in the study.

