11. PROCEDURES INVOLVED*

Non-vaper participants (regardless of their susceptibility) will first complete the online consent (i.e., STUDY00001220-Screener Consent_Fact Sheet_04.06.24.docx) and screener survey on

INVESTIGATOR STUDY PLAN - REQUIRED

Qualtrics to determine their eligibility for susceptibility and will receive \$1.00 via Prolific for participating in a 5-minute study. We will use the list of eligible participants from the screener survey, who will have been identified as susceptible, to participate in the 20-minute study, as described below.

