24. LOCAL RECRUITMENT METHODS

We will recruit U.S. young adults (N=800; 18-24 years) identified as vapers (n=400) and susceptible non-vapers (n=400) to collect self-report measures. Vapers are defined as those who have vaped in the past 30 days,^{2,55} and susceptible non-vapers are defined as those who have never vaped, or those who have ever vaped but not in the past 30 days, but are susceptible to use as determined by the Susceptibility to Use Tobacco Products questionnaire.⁵⁶ We will use Prolific, a crowdsourcing platform.⁵⁷ Prolific is optimal for this type of behavioral experiment⁵⁸ because it allows a rapid collection of high quality data.⁵⁷ Our team has successfully recruited participants and completed studies using Prolific.^{59,60} Using an online convenience sample has yielded comparable results with probability samples in prior tobacco survey research studies.^{61,62} We will use Prolific's screening features to recruit participants based on their vaping status (vapers and susceptible non-vapers), age (18-24 years), English fluency, and location (U.S.). We will use all data assurance measures (e.g., attention checks, manual review, bot inspection) for data quality, as we have done in past crowdsourced studies.^{59,63} Participants sign up to be on the

INVESTIGATOR STUDY PLAN - REQUIRED

Prolific platform as participants and can self-select what studies they want to participate in. However, the study will not use advertisements to directly recruit participants for this study. Participants who complete the study will receive \$4.00 via Prolific per its policies for participating in a 20-minute survey. This study will not be advertised specifically to recruit UMass Chan students. It is possible that UMass Chan students who signed up to be on the Prolific platform might participate in the study.

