## Crowdsourcing Study

**Study Design and Power Analysis:** The focus of this proposal is to assess which communication principles influence self-reported responses on source trust, psychological reactance, message liking, attitudes, and behavioral intentions of young adults. Eligible participants will complete an online consent and tobacco use questions on a Qualtrics survey before random assignment to one of four experimental conditions in a 2 (Source: expert and peer) X 2 (Presentation: one-sided and two-sided) design. For the crowdsourcing study of Aim 1, we wish to identify top-rated features to be tested further using psychophysiological testing. We investigated the stability of ranks as a function of number of participants, using simulated data (500 sets of simulated data per run) based on observed outcome distributions from Stevens et al. (2021). These runs indicated that ranks for the top 3 features are stable with 50 participants each receiving 18 messages. Separately for vapers and susceptible non-vapers, within each of 8 possible conditions (2 expert types x 2 peer types x 2 presentation types) we will recruit n=50 participants, or n=400 for each vaping status and n=800 total. Scores for each measure will be summed and averaged across all messages within each vaping status condition. I will use a multi-attribute decision-making (MADM) framework to produce a dataset containing data on participant response to each message with source + presentation type. I will merge crowdsourced and psychophysiological data to rank messages and determine optimal content.

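### Are 640 screened non-vapers too few to yield 400 susceptible ones?

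*Protocol*

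**What the plan says.** Protocol Section 6 states "We expect that we will need 640 number of people identified as non-vapers to complete the screener" and ties that number to having a complete sample for the 20-minute study. It gives no susceptibility rate, return rate or derivation.

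The target is consistent throughout. Section 6 splits the 800 participants as "50% current vapers and 50% susceptible non-vapers". Section 24 has participants "identified as vapers (n=400) and susceptible non-vapers (n=400) to collect self-report measures". The SAP builds the same number from eight conditions: "we will recruit n=50 participants, or n=400 for each vaping status and n=800 total".

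On who is screened, Section 11 says "Non-vaper participants (regardless of their susceptibility) will first complete the online consent", followed by the screener. On who qualifies, Section 24 says "susceptible non-vapers are defined as those who have never vaped, or those who have ever vaped but not in the past 30 days", provided they are susceptible on the questionnaire. Section 5 has the only prevalence figures in either document, for U.S. 18-24-year-olds: "16-19% of this population identifying as current users, 44-48% ever users, and 11-16% susceptible never users".

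**The concern.** Dividing the target by the expected screens gives a yield of 62.5%, which neither document states. A reader who tries to rebuild it from Section 5 falls short: even if every former vaper is counted as susceptible, the figures seem to stop at 57.1%. The screener and the main survey are also separate steps, so some people will not come back. Section 24 adds "We will use all data assurance measures (e.g., attention checks, manual review, bot inspection) for data quality", which implies that some completed surveys will be discarded.

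If recruitment stopped at 640 screens with a 57.1% yield, the susceptible non-vaper group would have about 46 people per condition instead of 50. The SAP's only sample-size argument is that the top three ranks are stable with 50 participants each seeing 18 messages, so a shortfall would eat into that justification.

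**Working it through.** **Inputs.** Expected screens 640 (Section 6). Target 400 (Sections 6 and 24; SAP, 8 conditions x 50). Current users 16-19%, ever users 44-48%, susceptible never users 11-16% (Section 5). Screener payment $1.00 (Section 11).

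**1. The plan's own figure.** 400/640 = 62.5%. With no stated yield, 640 can only be solved backwards. The 62.5% combines three things: being susceptible, returning, and giving valid data.

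**2. Yield from Section 5.** If ever users include current users, former vapers are ever minus current, and

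yield = [(ever - current) x share of former vapers susceptible + susceptible never] / (100 - current).

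The most favourable ends of the ranges, with all former vapers susceptible, give (48 - 16 + 16)/(100 - 16) = 48/84 = 57.1%. Then 400/0.5714 = 700 screens. At that yield, 640 screens give 640 x 0.5714 = 366, or 366/8 = about 46 per condition, 34 short in total.

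**3. How far this depends on the reading.** Over all eight combinations of range ends, before any loss:

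| Reading of Section 5 | Yield | Screens for 400 |
|---|---|---|
| Ever includes current; all former vapers susceptible | 44.4% to 57.1% | 900 to 700 |
| Ever includes current; half of former vapers susceptible (assumption) | 29.0% to 38.1% | 1379 to 1050 |
| Ever excludes current; all former vapers susceptible | 65.5% to 79.0% | 611 to 507 |

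The first reading of ever users is the usual one and fits the definition in Section 24. Section 5 does not state it, and under the third row 640 is enough.

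**4. How far the screener would have to differ from Section 5.** Keep the first row's best case. For 640 to suffice, the rate among never users must be (0.625 x 84 - 32)/52 = 39.4%. Section 5 implies 16/52 = 30.8%. The gap is under 9 percentage points, between two different populations. The instrument may differ too: Section 5 does not describe the measure behind its 11-16%, whereas Section 6 treats responses above the lowest scale point as susceptibility and includes an item on ever having been curious.

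**5. Loss after screening.** The documents give no rate, so these are assumptions. If 90% or 80% return and pass the checks, 62.5% susceptibility needs 400/(0.625 x 0.9) = about 711 or 400/(0.625 x 0.8) = 800 screens. At 57.1% the numbers are about 778 and 875.

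**6. Cost of being wrong.** Extra screens cost $1.00 each: 700 - 640 = $60; 875 - 640 = $235; 1379 - 640 = $739 in the least favourable row of the table.

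**The case for a change.** The strongest argument for a change is that 57.1% already favours the sponsor. It takes the best end of every range and counts all former vapers as susceptible, yet it still misses 62.5%. If 57.1% were the true yield, the binomial chance of 400 or more from 640 would be about 0.3%. The loss argument does not depend on Section 5 at all: even a correct 62.5% leaves no room for people who do not return or fail the checks. No sentence says that screening continues until 400 valid completions are in hand.

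Part of this stands. The 640 has no stated source, and no loss allowance is shown. What does not stand is the claim that the protocol contradicts itself. 57.1% is a ceiling only if general-population rates carry over to this pool and this instrument. The 0.3% further requires that screening stop at exactly 640, which no text says.

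Nor is it settled that the pool is an unselected one. Section 11 has non-vapers screened whatever their susceptibility. Section 24, however, says Prolific's own filters will be used to recruit by vaping status, with susceptible non-vapers named as a category, and Section 6 says Prolific supplies people eligible for each category. The documents point both ways, so some enrichment cannot be ruled out.

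The missing instruction to keep screening is a gap, but the target of 400, repeated in both documents, already tells the team when the group is full.

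**Conclusion.** No change is needed. The 62.5% is correctly derived and unsupported by any stated source, but the documents do not show 640 to be wrong. The apparent shortfall of 34 people, or 60 screens, rests on three assumptions: that Section 5's national rates apply to Prolific members answering this screener, that ever users include current users, and that every former vaper is susceptible. Relaxing the first or second can remove the shortfall; relaxing the third makes it larger.

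In every case the consequence is the same. The 640 is a planning expectation, while 400 susceptible non-vapers, at 50 per condition, is the recruitment commitment. A team following the plan would keep screening until that number is reached, at $1.00 and about five minutes per additional person. Writing down a yield, its source and a larger forecast would alter no enrolled number, comparison, ranking or conclusion.

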Eligible participants will complete an online consent (STUDY00001220-Consent_Fact Sheet.v3.013124.docx) and tobacco use questions on a Qualtrics survey before random assignment to one of four experimental conditions in a 2 (Source: expert and peer) X 2 (Presentation: one-sided and two-sided) design. First, participants will view the source description within their assigned condition and view 18 random-ordered messages. See Appendix A. Copies of the messages. They will rate each message for perceived message effectiveness (PME),⁴⁵ a widely used measure of message acceptance by the FDA's tobacco health communication campaigns.^{46,47} They will also rate e-cigarette harm perceptions,⁴⁸ psychological reactance (resistance to the message),⁴⁹ message liking,^{50,51} and source trust.⁵² The process will repeat 18 times, once for each message. Afterwards, participants will complete posttest survey questions about their demographics, attitudes about vaping,⁴⁶ and behavioral intentions to vape.⁵³ We will check manipulation of the source manipulation by asking participants to indicate the source of the message they saw after the first three messages. After completing the study, they will receive \$4.00 via Prolific per its policies for participating in a 20-minute survey. At the end of the study, participants will be extensively debriefed about the hypothetical nature of the message source and the health harm of using any tobacco products, provided with an information sheet about the health effects of e-cigarettes and resources for the Quitlines across the U.S. See Appendix B-1 and B-2 for information about nicotine health harms and resources to quit. They will also complete a questionnaire assessing their understanding of the information regarding quitting resources. At the end of the survey, each participant is given a unique code to input into Prolific to receive compensation. We will double-check responses on our end of the survey and approve them to compensate participants.

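### Vaping status comes from platform filters, and no rule checks it against the protocol's past-30-day definition; any misclassification would dilute the results by status

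*Protocol*

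**What the plan says.** **Definition.** Protocol section 24: "Vapers are defined as those who have vaped in the past 30 days". Susceptible non-vapers are "those who have never vaped, or those who have ever vaped but not in the past 30 days, but are susceptible to use", with susceptibility determined by a questionnaire.

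**Source of status.** Section 6 says that the platform supplies people in each recruited category, that the team selects them by setting preferences, and that "We do not need to screen the participants for this". Section 24 likewise relies on the platform's "screening features to recruit participants based on their vaping status (vapers and susceptible non-vapers").

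**Study screener.** Section 6: "We will screen for e-cigarette use susceptibility of non-vaper participants". Section 11 confirms that it goes to non-vapers only. The four listed items cover curiosity, likelihood of trying an e-cigarette (soon, and within a year) and response to a friend's offer. None asks about use in the past 30 days.

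**Main survey.** Under section 11, participants already called eligible answer "tobacco use questions on a Qualtrics survey before random assignment to one of four experimental conditions". Neither document says what happens when an answer disagrees with the filter.

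**Analysis.** Protocol section 13 and the SAP average scores by vaping status and then rank message types. Neither says whether the filter or the survey answer defines status.

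**The concern.** Vaping status is the variable that separates the two populations, and every planned result is reported by it. The protocol expects opposite answers in the two groups. Section 4 predicts that expert and one-sided messages do better in susceptible non-vapers. The matching hypothesis for vapers in section 4 is garbled, but the background in section 5 points to peer and two-sided messages. If that theory is right, a person placed in the wrong group does more than add noise: they pull that group's means towards the other group's answer.

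The boundary is also easy to cross. It is a rolling 30-day window, and people who have vaped, but not recently, are deliberately included among the non-vapers. The susceptibility screener gives no protection, because a current vaper in the non-vaper stream would be expected to pass it.

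**Working it through.** **1. The plan's own figure.** The SAP has 4 source types (two expert, two peer) × 2 presentations = 8 conditions; 8 × 50 = 400 per status; 400 × 2 = 800. This reproduces. The choice of 50 rests on a rank-stability simulation whose outcome distributions are not given, so it cannot be re-run.

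**2. What tests status in each stream.**

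| Stream | Platform filter | Study screener | Tobacco use questions | Rule using the answers |
|---|---|---|---|---|
| Vapers | yes | none | yes, before randomisation | none stated |
| Non-vapers | yes | susceptibility items only | yes, before randomisation | none stated |

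**3. Dilution.** Let d be the true effect in a group, m the share of that group who belong to the other one, and −k·d the effect in the other group. Then

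observed effect = d × [(1 − m) − m·k].

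Neither m nor k is in the documents; the values below are assumptions. Share of the true effect kept:

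| m | People of 400 | k = 1 (equal and opposite) | k = 0.5 | k = 0 (no effect in other group) |
|---|---|---|---|---|
| 5% | 20 | 90% | 92.5% | 95% |
| 10% | 40 | 80% | 85% | 90% |
| 20% | 80 | 60% | 70% | 80% |

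The difference in effect between vapers and non-vapers shrinks by the factor 1 − m(vapers) − m(non-vapers), for example to 80% with 10% in each group.

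**4. Cancellation.** The observed effect reaches zero at m = 1/(1 + k): 50% for k = 1, 67% for k = 0.5, 33% for k = 2. If k = 0 there is dilution only.

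**5. Ranks.** With k = 1, every contrast is multiplied by 1 − 2m, so the expected order of message types is unchanged for m below 50%. What suffers is separation relative to noise. As an illustration, take two of the four source-by-presentation types within one status (400/4 = 100 people each) and an assumed true difference of 0.28 SD. The chance that they come out in the right order is Φ[(1 − 2m) × 0.28/√(2/100)]: 0.976 at m = 0, 0.943 at 10% and 0.883 at 20%. Keeping the original separation would need 400/0.8² = 625 per status at m = 10%, or 400/0.6² = 1111 at m = 20%.

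**6. The screener can concentrate the error.** Section 6 expects 640 non-vapers to be screened and 400 are wanted, a yield of 400/640 = 62.5%. Suppose 5% of the 640 (32 people) are really current vapers and all of them pass. They are then 32/400 = 8% of the analysed group. With 10% (64 people) the share is 16%. This too is illustrative.

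**The case against.** The strongest reply is that the study does collect the information. Every participant answers tobacco use questions before randomisation. Section 11 has the team double-check responses before approving payment, and section 24 promises: "We will use all data assurance measures (e.g., attention checks, manual review, bot inspection) for data quality". The only definition of a vaper in the protocol is past-30-day use, so analysing by survey answer would be fully consistent with the text. The questionnaire is not in the documents and might already contain the item and a branch. The platform filter might itself use a 30-day window. No hypothesis test or power target is planned, and the expected ranks survive moderate misclassification.

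Much of this stands, and it rules out several stronger readings that a reader might draw:

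- *Vapers have no check at all.* Not supported: tobacco use is asked of everyone. What is missing is a rule for using the answers.
- *Participants will be analysed in the wrong population.* Not supported: the documents leave the defining source open and do not prescribe the filter for analysis.
- *Platform profiles are out of date.* Not shown: the filter's wording, look-back period and update interval are not given.
- *Susceptibility is not screened.* Not so: sections 6 and 11 describe a study screener. Only the parenthesis in section 24, which lists susceptible non-vapers under platform filters, needs reconciling with them.

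The reply does not supply the missing rule. None of the named data-quality measures is said to verify vaping status, and section 6 states outright that screening is unnecessary.

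**Conclusion.** The point holds as a should-change item. As written, eligibility by vaping status rests on platform filters, and nothing in either document ties the pre-randomisation answers to eligibility or to the analysis group. The protocol therefore cannot show that its groups meet its own definition.

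Any misclassified share m would leave 1 − 2m of the within-status differences if effects are equal and opposite, or 1 − m if the other group has none: 80% or 90% at 10%, and 60% or 80% at 20%. Ranks would be less stable, although their expected order would not change for m below 50% in the equal-and-opposite case. All of this rests on assumed m and k, and the vaper direction comes from background text that is worded tentatively.

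A reader might infer that opposite effects would cancel. The arithmetic does not support that: it takes about a third to two thirds of a group misclassified for k between 2 and 0.5, and even 20% with equal and opposite effects keeps 60%.

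**What to change.** - **Section 6.** Replace "We do not need to screen the participants for this" with a statement that platform filters only pre-select participants, and that past-30-day use is confirmed from the tobacco use questions in the study's own survey before randomisation. Make sure those questions include a past-30-day item.
- **Section 11.** State that anyone whose answer does not match their recruitment stream is screened out before randomisation and replaced. Screening out is simpler than moving people between streams, because those recruited as vapers have not completed the susceptibility items.
- **Protocol section 13 and SAP.** State that survey-reported status defines the analysis group.
- **Section 24.** Reword so that filters cover vaping status, age, language and location, and susceptibility comes from the screener.

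The cost is one survey branch, a few sentences, and replacement recruitment in proportion to the discordance found. That could be more than a handful: 5% to 20% of a group of 400 is 20 to 80 people. The number screened out would also give the study its own estimate of how often filter and survey disagree.
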